### 953 **5.1.4 Visit and Phone Contact Schedule during Study Periods 1 and 2**

954 During each of the two study periods, visits and contacts will be scheduled as outlined below.  
955 Additional contacts or visits may occur as needed:

- 956 • Study Period begins
  - 957 ○ 6-10 days – participants will be contacted by phone to ensure auto mode is  
958 initialized
  - 959 • Auto mode is initialized (remaining visits and contacts are relative to the day auto mode  
960 is confirmed to be initialized by site staff)
    - 961 ○ 24-hour contact (*Contact must be completed by phone*)
    - 962 ○ 5-day contact ( $\pm 2$  days) = 3-7 days (*Contact must be completed by phone*)
    - 963 ○ 2-week visit ( $\pm 4$  days) = 10-18 days
    - 964 ○ 4-week contact ( $\pm 4$  days) = 24-32 days
    - 965 ○ 6-week visit ( $\pm 4$  days) = 38-46 days
    - 966 ○ 9-week contact ( $\pm 4$  days) = 59-67 days
    - 967 ○ 12-week visit/contact (+7 days) = 84-91 days (end of study period)

968 The goal will be for all participants to complete all scheduled visits. However, participants who  
969 (because of unforeseen circumstances) are unable or unwilling to return for all follow-up visits  
970 will be permitted to return for key visits only as an alternative to withdrawal from the study.  
971 When a participant is placed into this status, missed visits will not be recorded as protocol  
972 deviations (since they would not be recorded as protocol deviations if the participant was  
973 dropped from the study).  
975

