1755 will be conducted for severe hypoglycemia and diabetic ketoacidosis events outcomes. For binary  
1756 variables, repeated measures logistic regression which adjust for period, pre-study 670G system  
1757 use, HbA1c at randomization, and whether the participant experienced any events in the 12 months  
1758 prior to enrollment as fixed effects will be used to compare treatment groups. For counts, such as  
1759 the number of severe hypoglycemic or diabetic ketoacidosis events per participant, data will be  
1760 compared using repeated measures Poisson regression with period, pre-study 670G system use,  
1761 HbA1c at randomization, and whether the subject experienced any events in the 12 months prior  
1762 to enrollment as fixed effects adjusted in the model. All participants will be included in these  
1763 analyses.

1764

1765 **10.9 Adherence and Retention Analyses**

1766 Tabulations and figures by treatment period to assess protocol adherence will include:

- 1767 • Flowchart showing any dropouts prior to and post randomization and treatment arm  
1768 completion
- 1769 • Visit completion rates for each follow up visit
- 1770 • Protocol deviations
- 1771 • Numbers and reasons for unscheduled visits and phone calls

1772

1773 **10.10 Baseline Descriptive Statistics**

1774 Baseline demographic and clinical characteristics will be tabulated by randomization group.

1775

1776 **10.11 Planned Interim Analyses**

1777 No formal interim analyses or stopping guidelines are planned for this study.

1778  
1779 The DSMB will review data for safety per the DSMB Standard Operating Procedures  
1780 approximately every six months. The data to be reviewed will include information regarding  
1781 adverse events, device issues, and protocol adherence/ deviations as they may relate to participant  
1782 safety.  
1783  
1784 **10.12 Sub-Group Analyses**  
1785 Exploratory subgroup analyses/assessments of effect modification (interaction) will be  
1786 conducted for each of the two primary outcomes. Interpretation of the analyses will be made with  
1787 caution, particularly in the absence of an overall difference. The general approach for these  
1788 exploratory analyses will be to add an interaction term for the subgroup factor by treatment into  
1789 the model used for the primary analysis.  
1790  
1791 The following baseline factors will be assessed:  

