91 12) Total Basal Insulin Units per Kilogram of Weight

92 13) Total Bolus Insulin Units per Kilogram of Weight

93 HbA1c Metrics

94 14) HbA1c

95 Clinical Metrics

96 15) BMI

97 Additional Exploratory Endpoints:

98 CGM Metrics:

99 *Continuous Outcomes:*

100 1) Time below 50 and 60 mg/dL

101 2) Time above 300 mg/dL

102 3) Area under the curve of sensor glucose levels above 180 mg/dL

103 4) Area over the curve of sensor glucose levels below 70 mg/dL

104 5) Standard deviation of sensor glucose levels

105 *Binary Outcome:*

106 1) Time in range (70-180 mg/dL) >70% and time below 54 mg/dL <1%.

107 HbA1c Metrics:

108 *Binary Outcomes:*

109 1) Improvement in HbA1c  $\geq 0.5\%$

110 2) Improvement in HbA1c  $\geq 1.0\%$

111 3) Relative reduction in HbA1c  $\geq 10\%$

112 4) HbA1c  $< 7.0\%$

113 All secondary efficacy and exploratory CGM metrics will be calculated over each treatment  
114 period for the full 24 hours, daytime (6:00 AM – 11:59 PM), and nighttime (12:00 AM – 5:59  
115 AM). They also will be calculated for each post-meal period measured for up to three hours after  
116 the start of a meal. The same will be done for all secondary efficacy insulin endpoints. It is

117 important to note that all hypoglycemic outcomes are considered both efficacy and safety  
118 outcomes.

119 **4.1 Calculation of the Co-Primary Outcomes**

120 As noted above, the co-primary outcomes are:

121 • Daytime Hyperglycemia (percent CGM readings above 180 mg/dL)  
122 • Hypoglycemia (percent CGM readings below 54 mg/dL; daytime/nighttime combined)

123 For each co-primary outcome, a single value will be calculated for each subject for each period  
124 by pooling all CGM readings in the first 84 days of each period or up to and including the 12-  
125 week visit date (whichever comes first).

126 In these calculations, each period will start at the time that the subject turns on auto mode. If the  
127 exact time is not known, then the period will start at midnight the day after the subject initiates it.  
128 We expect auto mode to be initiated 6-10 days after the randomization visit in period 1 and 6-10  
129 days after the first day of period 2. Participants who are 670G auto mode users at screening may  
130 initiate auto mode at the beginning of a study period in which the 670 3.0 HCL pump is being  
131 used. The end of the period will be defined as either 11:59 PM on the 12-week visit date or  

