## 331 **8.3 Comparison of Safety Outcomes between Treatment Arms**

332 Each of the following safety outcomes will be tabulated by treatment arm:

- 333 • Number of adverse events/participants with at least one event
  - 334 ▪ Number of events meeting definition of ADE
- 335 • Number of serious adverse events/participants with at least one event
  - 336 ▪ Number of SAEs meeting definition of UADE
- 337 • Listing of hospitalizations and reasons for the hospitalization
- 338 • Severe Hypoglycemic Events
  - 339 ▪ Number of severe hypoglycemic events as defined in the protocol/number of  
340 participants with an event
  - 341 ▪ Number of severe hypoglycemic events associated with seizure or loss of  
342 consciousness/number of participants with at least one event
- 343 • Diabetic Ketoacidosis
  - 344 ▪ Number of diabetic ketoacidosis events, as defined in the protocol/number of  
345 participants with an event

346 Of the outcomes listed above, only the ones involving SH or DKA events will be compared  
347 between treatment arms, if there are at least five events across the two treatment arms. The others  
348 will only be tabulated by treatment arm.

349 All of the above safety outcomes will be tabulated for all subjects (including dropouts and  
350 withdrawals) for their entire period of study participation. Any adverse events that occurred prior  
351 to the start of period 1 (as defined above) will not be included in the treatment arm comparisons  
352 listed above. Each period will inclusively consist of all days in between the start of the period  
353 and the 12-week visit date.

354 If there are enough SH and DKA events associated with each treatment arm to allow for formal  
355 statistical modeling, then treatment arm comparisons will be performed for the SH and DKA  
356 outcomes listed above. For binary outcomes, repeated measures logistic regression models  
357 adjusting for period, pre-study 670G system use, HbA1c at randomization, and whether the  
358 subject experienced any events in the 12 months prior to enrollment will be used to compare  
359 treatment groups. If the model does not converge, a mid-p binomial test will be considered. For  
360 counts, the treatment groups will be compared using repeated measures Poisson regression  
361 models adjusting for period, pre-study 670G system use, HbA1c at randomization, and whether  
362 the subject experienced any events in the 12 months prior to enrollment.

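### The Poisson model for severe hypoglycemia and DKA counts names no person-time offset, so it compares counts per period rather than rates; the effect is small and arises only if follow-up is unbalanced

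*SAP*

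**What the plan says.** **Model.** SAP 8.3 states that for "counts, the treatment groups will be compared using repeated measures Poisson regression" models, adjusted for period, pre-study 670G use, HbA1c at randomization and any event in the 12 months before enrollment. Protocol 10.8 has events per participant "compared using repeated measures Poisson regression with period, pre-study 670G system use" and the same remaining covariates. Neither section mentions an offset, time at risk or a rate. The tables in both give numbers of events and numbers of participants with an event. The SH/DKA comparison is made only if there are enough events; SAP 8.3 sets a minimum of five across both arms.

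**Who is counted.** SAP 8.3: "All of the above safety outcomes will be tabulated for all subjects (including dropouts and" withdrawals). Protocol 10.8, on the models: "All participants will be included in these" analyses.

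**Length of the safety period.** SAP 8.3: "Each period will inclusively consist of all days in between the start of the period" and the 12-week visit date. SAP 4.1 gives the start: "In these calculations, each period will start at the time that the subject turns on auto mode". Protocol 5.1.4 places the end at "12-week visit/contact (+7 days) = 84-91 days (end of study period"). The 2,016-hour cap in SAP 4.1 is written for the CGM outcomes and is not repeated in SAP 8.3.

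**Prior 670G auto-mode users.** Under SAP 4.1 they may "initiate auto mode at the beginning of a study period in which the 670 3.0 HCL pump is being" used. Everyone else, and these participants in their AHCL period, waits 6-10 days.

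**The concern.** An event count grows with time at risk. A Poisson model without an offset gives every participant-period the same weight of exposure, so someone who leaves two weeks into a period is treated as having been observed, event-free, for the rest of it. The co-primary outcomes do not share the problem, because they are percentages of the readings obtained. A dropout may also have no 12-week visit, and SAP 8.3 then gives no end date for that period.

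The comparison at stake is that of SH and DKA between an investigational insulin algorithm and its active control. It should not shift because one arm was followed for less time. No efficacy conclusion depends on it.

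**Working it through.** The documents give no expected event count, event rate or power for SH or DKA, so there is no figure of the plan's own to reproduce on this point.

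**Inputs from the documents**
- About 112 enter the crossover and at least 100 complete (Protocol 2.1; SAP 1): 112 - 100 = 12 planned dropouts, 12/112 = 10.7%.
- 12-week visit on day 84-91 after auto mode, the same window in both arms (Protocol 5.1.4); midpoint 87.5 days.
- Recruitment goal of at most 25% on the 670G at screening (Protocol 2.1); auto mode otherwise starts after 6-10 days.

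**Assumptions, not in the documents:** how the 12 dropouts split between arms and when they leave.

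**Formula.** Suppose the true event rates are equal. The expected count per record is the rate times mean person-time per record, so the ratio estimated without an offset is

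mean person-time per AHCL record / mean person-time per 670G 3.0 record.

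With log(person-time) as an offset it is 1.00. Here f is the fraction of the period observed before leaving. Unless stated otherwise, all 112 participants have a record in each arm, which means the dropouts leave in Period 2.

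| Scenario | AHCL / 670G 3.0 | Ratio without offset |
|---|---|---|
| Dropouts and visit timing balanced | equal | 1.00 |
| Dropouts split 8:4 against AHCL, f = 0.5 | (104 + 8 x 0.5)/(108 + 4 x 0.5) = 108/110 | 0.98 |
| Same split, f = 0 | 104/108 | 0.96 |
| All 12 leave AHCL, f = 0.5 | (100 + 12 x 0.5)/112 = 106/112 | 0.946 |
| All 12 leave AHCL, f = 0 (extreme bound) | 100/112 | 0.893 |
| Every AHCL visit on day 84, every 670G 3.0 visit on day 91 (not realistic) | 84/91 | 0.92 |

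Swapping the arms inverts each ratio. If instead all 12 leave halfway through AHCL in Period 1 and the period never started gives no record, a fit with treatment and period terms gives 0.94, close to the 0.946 above.

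**Effect on inference.** Given E events in total and equal true rates, the number on AHCL is binomial with probability r/(1 + r), where r is the exposure ratio. For r = 0.946 this is 0.486. An exact binomial test against 0.5 approximates the planned model. The chance of a false finding in favour of the shorter arm is:

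| Total events | r = 1 | r = 0.946 | r = 0.893 |
|---|---|---|---|
| 20 | 2.1% | 2.8% | 3.7% |
| 40 | 1.9% | 2.9% | 4.3% |

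At the five-event minimum even a 0:5 split gives two-sided p = 2 x 0.5^5 = 0.0625. In that test the missing offset cannot create a significant result.

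**The case against.** **The plan is silent on an offset and does not exclude one.** SAP 8.3 lists what the models adjust for, and an offset is not an adjustment covariate. That is fair as a reading of the sentence. But no rate, person-time or offset appears anywhere in the safety sections, and the tables are counts too, so an analyst following the text would produce a comparison of counts.

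**The design limits the bias.** Treatment order is randomized 1:1 and each completer contributes to both arms. Under Protocol 8.5.1 and 9.5, a participant who stops the device is still encouraged to stay in the study, and SAP 5.1 keeps each period in its assigned arm. Only full withdrawal loses time at risk, and the SAP 9 flowcharts would show an imbalance. All of this stands, and it is why the effect is small.

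**Stronger readings that the documents do not support.**
- *Follow-up differs by arm by design.* A reader might infer this from the early auto-mode start allowed to prior 670G users. But the period rule is the same in both arms, and footnote 1 of Protocol Table 2 ties all follow-up visits to the day auto mode is initialized, so an earlier start brings an earlier 12-week visit. The 670G 3.0 period is longer only if visits run from a later confirmation by site staff, which is one reading of Protocol 5.1.4. On that reading, with the full 25%, the ratio is 87.5/(87.5 + 0.25 x 6) = 0.98 to 87.5/(87.5 + 0.25 x 10) = 0.97.
- *The bias flatters AHCL.* This needs dropout concentrated in AHCL periods, and nothing in the documents indicates that.
- *The ratio could be inflated to 106/100 = 1.06* if all 12 leave halfway through AHCL in Period 1. This holds only if 670G 3.0 periods that were never started are entered as zero-count rows. The SAP does not say that they are.

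**Conclusion.** The point holds as a minor gap in a conditional safety analysis. The Poisson model in SAP 8.3 and Protocol 10.8 compares counts per period, while partial periods are included and full periods may run from 84 to 91 days. Any imbalance in follow-up passes directly into the ratio, in favour of the arm with less follow-up.

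If the true rates are equal, the distortion is nil with balanced follow-up, about 0-5% in plausible scenarios and about 11% at the extreme. These sizes rest on the planned 12 dropouts and on assumed splits and timings; the direction cannot be known in advance. With few events, a shift of this size is small beside the sampling error. It is a free improvement, not a threat to the trial's conclusions.

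**What to change.** In SAP 8.3 and Protocol 10.8:

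1. Add log(person-time in the period) as an offset to the Poisson models for SH and DKA.
2. Define person-time from the start of the period to the earlier of the 12-week visit and the last contact. A period never started gives no record. Use the same boundaries for events and for person-time, and state how the manual-mode days before auto mode are treated.
3. Report SH and DKA events per 100 person-years, with person-time by arm, beside the counts.

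The cost is a few sentences and one model term. The auto-mode, visit and contact dates are already collected. With person-time defined this way, the result no longer depends on which day the visits of prior 670G users were counted from.

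**Label:** free improvement.

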## 363 **9. Adherence and Retention Analyses**

364 The following tabulations will be performed by treatment arm to assess protocol adherence for  
365 this study:

- 366 • Number of protocol deviations by severity with brief descriptions listed for each  
367 treatment arm
- 368 • Number of and reasons for unscheduled visits and phone calls for each treatment arm

369 Additionally, the following two flowcharts will be created:

- 370 • Flowchart displaying all dropouts prior to and post randomization in addition to treatment  
371 arm completion to assess dropout rates
- 372 • Flowchart displaying the number of subjects completing and missing each visit by  
373 treatment arm to assess visit completion rates

## 374 **10. Baseline Descriptive Statistics**

375 Baseline demographic and clinical characteristics of the cohort of all randomized subjects will be  
376 summarized in a table. Descriptive statistics will be tabulated overall and by randomization  
377 group. For continuous variables, summary statistics appropriate to the distribution will be given.  
378 For discrete variables, number and percentage will be reported for each category.

379 The following baseline CGM metrics will be included in a separate table:

- 380 • Percentage of time in the target range (70-180 mg/dL)
- 381 • Mean glucose
- 382 • Coefficient of Variation
- 383 • Percentage of time below 54 mg/dL and below 70 mg/dL
- 384 • Percentage of time above 180 mg/dL and above 250 mg/dL
- 385 • Percentage of time above 180 mg/dL during the daytime (6:00 AM – 11:59 PM)
- 386 • Percentage of time above 180 mg/dL during the nighttime (12:00 AM – 5:59 AM)

387 These baseline metrics will be calculated in the manner described in sections 4.1 and 4.2.

388 Additionally, each of these baseline metrics will be calculated for the post-meal periods as  
389 described in section 4.2.1, and will be reported in another table.

## 390 **11. Planned Interim Analyses**

391 No formal interim analyses or stopping guidelines are planned for this study.

392 The DSMB will review data for safety per the DSMB Standard Operating Procedures  
393 approximately every six months. The data to be reviewed will include information regarding  
394 adverse events, device issues, and protocol adherence/deviations as they may relate to participant  
395 safety.

## 396 **12. Subgroup Analyses**

398 The treatment effect in subgroups based on baseline factors will be assessed for each co-primary  
399 outcome. These analyses will be considered exploratory and will be conducted to determine  
400 whether a similar trend to the overall treatment effect is seen in these subgroups. Assessment of  
401 subgroup analyses will be interpreted with caution, particularly if the primary analysis does not  
402 show significant results. The general approach for these subgroup analyses will be to add an

403 interaction term for the subgroup factor by treatment into the model used for the primary  
404 analysis.

405 The following baseline factors will be assessed:

- 406 • Age: as a continuous variable and in 2 age groups: 14-<21 and 21-<30 years old
- 407 • Baseline HbA1c: as a continuous variable and in 2 groups: HbA1c  $\leq 8.5\%$  and  $\geq 8.6\%$
- 408 • Insulin method/CGM: 670G user, injection user with CGM, injection user without CGM,  
409 pump user with CGM, and pump user without CGM
- 410 • T1D duration as a continuous variable
- 411 • Gender
- 412 • Race/ethnicity
- 413 • Random C-peptide level

414 Cut points for dichotomizing T1D duration and random C-peptide level variables will be set to  
415 be the medians for display purposes.

416 In addition to the assessment for interaction, the co-primary analyses and all secondary analyses  
417 described in sections 6 and 7 will be conducted separately in the two age groups and two HbA1c  
418 groups. Analyses will only be replicated within these subgroups for efficacy outcomes where p-  
419 values are being calculated. Exploratory endpoints will not be calculated within these subgroups.

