## Chapter 2: Study Enrollment and Screening

### 615 2.1 Participant Recruitment and Enrollment

616 Enrollment will proceed with the goal of at least 100 participants completing the crossover trial.  
617 A maximum of 135 individuals may be enrolled and a total of approximately 112 are planned to  
618 enter the crossover trial. Participants who have signed consent and started the screening process  
619 will be permitted to continue into the crossover trial, if eligible, even if the crossover trial  
620 randomization goal has been reached.

621

622 Study participants will be recruited from approximately seven clinical centers. All eligible  
623 participants will be included without regard to sex, gender, race, or ethnicity. All sites are  
624 experienced in either adult or pediatric endocrinology, or both, and are established research  
625 centers with proven recruitment track records.

626

627 The recruitment goal for each site is the same (approximately 15-16 participants per site);  
628 however, certain sites may recruit additional participants if necessary for the study to meet the  
629 overall recruitment goal.

630

631 In order to have a broad representation of individuals, there will be the following recruitment  
632 goals:

- 633 • Minimum of 25% of participants entering RCT who at screening were on MDI therapy
- 634 • Minimum of 25% of participants entering RCT who at screening were on Pump therapy
- 635 • Minimum of 25% of participants entering RCT who at screening were on CGM therapy
- 636 • Minimum of 25% of participants entering RCT who at screening were not on CGM therapy
- 637 • Minimum of 25% of participants entering RCT who at screening had a POC HbA1c from  
638 7.0 - 8.5%
- 639 • Minimum of 25% of participants entering RCT who at screening had a POC HbA1c from  
640 8.6 - 11.0%
- 641 • Maximum of 25% of participants entering RCT who at screening had a POC HbA1c from 7.0  
642 -7.4%
- 643 • Maximum of 25% of participants entering RCT who at screening were on the MiniMed 670G  
644 system

645

646 Potential eligibility may be assessed as part of a routine-care examination. Prior to completing  
647 any procedures or collecting any data that are not part of usual care, written informed consent  
648 will be obtained. For potential study participants  $\geq 18$  years old, the study protocol will be  
649 discussed with the potential study participant by study staff. The potential study participant will  

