### 1579 10.3 Sample Size

1580 The sample size calculation is detailed in a separate document and summarized below.

1581 For computing sample size, estimates of the standard deviation (SD) for time spent in  
1582 hypoglycemia and hyperglycemia were made based on data from previous studies, Medtronic  
1583 670G Pivotal Trial, DIAMOND, JDRF CGM RCT, and REPLACE-BG.

1584

1585 Analyses of both primary outcomes must have a significant result ( $p < 0.05$ ) to declare benefit of  
1586 the intervention. The two co-primary outcomes therefore do not inflate the type 1 error, but  
1587 requiring both to be significant can inflate the type 2 error. A Bonferroni correction was  
1588 therefore applied to the power calculations by adding the type 2 error rate (i.e., 100% minus  
1589 power) for the two analyses. This represents a conservative estimate for composite power as the  
1590 probability that both tests will reject the null hypothesis.

1591

1592 The total sample size was computed to be 65 for the following assumptions (1) 90% power, with  
1593 adjustment to account for the two co-primary analyses, (2) a 5% absolute reduction in time  $>180$   
1594 mg/dL (10.0 mmol/L) with a standard deviation of paired differences of 12%, and a 2-sided type  
1595 1 error rate of 5%, and (3) a non-inferiority limit of 2% for the treatment group comparison of  
1596 time  $<54$  mg/dL (3.0 mmol/L) with an SD of paired differences of 1.3% and 1-sided type 1 error  
1597 of 2.5%.

1598  
1599 A sample size of 100 completing the trial has been selected to provide increased precision for  
1600 safety analyses and subgroup analyses. With a sample size of 100 participants completing the  
1601 crossover trial, the primary analysis will have 98% power.

1602  
1603 **10.4 Outcome Measures**

1604 All CGM derived indices will be calculated over the first 84 days of each period. The beginning  
1605 of the period is defined as the time that auto mode is first turned on, which per protocol is 6-10  
1606 days after the period starts. A post-meal period is defined as follows: meal starts at the time the  
1607 carbohydrate is entered and post-meal period ends at three hours after a meal unless another  
1608 carbohydrate is entered  $<3$  hours, which is then considered the end of the post-meal period.

1609  
1610 Hypoglycemia metrics are considered both safety and efficacy outcomes.

1611  

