18   phase may vary depending on the participant's comfortability using the devices.

19   **2. Statistical Hypotheses**

20   In this study, there are two co-primary outcomes:

- 21   • Superiority in the percentage of time spent with sensor glucose levels above 180 mg/dL  
22   during the daytime (6:00 AM to 11:59 PM)
- 23   • Non-inferiority in the percentage of time spent with sensor glucose levels below 54  
24   mg/dL calculated over the full 24 hours of the day, with a non-inferiority limit of 2%  
25   based on clinical judgment.

26   Separate analyses will be performed for each co-primary outcome, and both analyses must  
27   produce a statistically significant result in order to declare benefit of the intervention.

28   For each of these analyses, the two corresponding pairs of null and alternative hypotheses are as  
29   follows:

30   Hyperglycemic Outcome:

- 31   • *Null Hypothesis:* There is no difference in the percentage of time spent with sensor  
32   glucose levels above 180 mg/dL between the two treatments during the daytime for the  
33   entire study population.
- 34   • *Alternative Hypothesis:* There is a nonzero difference in the percentage of time spent  
35   with sensor glucose levels above 180 mg/dL between the two treatments during the  
36   daytime for the entire study population.

37   Hypoglycemic Outcome:

38     • *Null Hypothesis*: There is a mean difference of at least 2% in the percentage of time spent  
39       with sensor glucose levels below 54 mg/dL between the AHCL system and the 670G  
40       system over the full 24 hours of the day for the entire study population.  
41     • *Alternative Hypothesis*: There is a mean difference of less than 2% in the percentage of  
42       time spent with sensor glucose levels below 54 mg/dL between the AHCL system and the  
43       670G system over the full 24 hours of the day for the entire study population.

44     **3. Sample Size**

45     The sample size calculation for this study is detailed in a separate document (in addition to the  
46       protocol) and summarized below. Sample size was calculated based on the following  
47       assumptions:

48     • 90% power  
49     • 5% true absolute reduction in percent time > 180 mg/dL during the daytime with a  
50       standard deviation of paired differences of 12% and a two-sided Type 1 error rate of 5%  
51     • Non-inferiority limit of 2% for the treatment group comparison of percent time < 54  

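### Secondary outcomes are tested within age and HbA1c groups, but interaction is tested only for the co-primaries, so the plan has no valid between-group comparison for them

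*SAP*

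**What the plan says.** SAP section 12 opens with the interaction assessment and limits it to the co-primaries: "The treatment effect in subgroups based on baseline factors will be assessed for each co-primary" outcome. These analyses are labelled exploratory, are to be read with caution, and are meant to show "whether a similar trend to the overall treatment effect is seen in these subgroups". The stated method is an interaction term added to the primary model.

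A later paragraph of the same section adds a second layer: "In addition to the assessment for interaction, the co-primary analyses and all secondary analyses" described in SAP 6 and 7 are repeated separately for ages 14-<21 and 21-<30 and for HbA1c ≤8.5% and ≥8.6%, for efficacy outcomes that have p-values. The exploratory endpoints are left out of this layer. Protocol 10.12 is built the same way, with interaction for the two primary outcomes and separate within-group runs of the primary and secondary analyses.

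SAP section 13 gives each of the four groups its own false discovery rate categories. The only interaction categories it lists are for the hyperglycemic and hypoglycemic outcomes.

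**The concern.** For time in range, mean glucose, insulin use, HbA1c and BMI, a reader of the subgroup tables will see a p-value for each group and nothing that compares the groups. Significance in one group and not in the other does not show that the effects differ. It is what a single common effect often produces once the sample is divided, above all when the groups are unequal in size.

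At stake is what the trial can say about adolescents versus young adults, and about lower versus higher HbA1c. These are the groups for which the plan itself asks for separate results. The co-primary conclusions and the full-cohort secondary analyses are not affected.

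**Working it through.** **Inputs.** Target reduction 5 points, SD of paired differences 12 points, two-sided 5% error (SAP 3, Protocol 10.3). Non-inferiority margin 2 points, SD 1.3, one-sided 2.5% (same places). Stated total of 65 for 90% power, and 98% power with 100 completers (Protocol 10.3). Protocol 2.1 sets a recruitment floor, "Minimum of 25% of participants entering RCT who at screening had a POC HbA1c from" each of two bands, 7.0-8.5% and 8.6-11.0%. No effect size or SD is given for any secondary outcome, and there is no recruitment goal for age.

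**The plan's own figure.** n = (SD × (z₀.₉₇₅ + z₀.₉₀) / δ)² = (12 × (1.960 + 1.282) / 5)² ≈ 60.5, so 61. The noncentral t gives 63, and power at 65 is 91.1%. The non-inferiority test needs about 5 patients, so its power is essentially 100% and adding the two type 2 errors costs nothing. At 100 completers the combined power is 98.5%, against the stated 98%. The stated figures are reproduced.

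**Uniform effect, plan's hyperglycemia inputs.** The two groups contain different patients, so their tests are independent. Let p₁ and p₂ be the noncentral-t power in each group. Then P(exactly one significant) = p₁(1 − p₂) + p₂(1 − p₁).

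| Split of 100 | Power in each group | Exactly one significant |
|---|---|---|
| 50 / 50 | 82% / 82% | 29% |
| 40 / 60 | 73% / 89% | 32% |
| 25 / 75 | 52% / 94% | 49% |

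For example, 50/50 gives 2 × 0.823 × 0.177 = 0.291. With 112 analyzed the three results are 23%, 26% and 44%.

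**Uniform effect, a secondary outcome.** Here overall power must be assumed. With overall noncentrality d = 1.960 + z(power), a group holding share f of the patients has noncentrality d√f and power Φ(d√f − 1.960).

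- Assumed 90% (d = 3.242). Equal groups: Φ(2.292 − 1.960) = 63% each, exactly one 2 × 0.63 × 0.37 = 47%. At 25:75: 36.7% and 80.2%, exactly one 0.367 × 0.198 + 0.633 × 0.802 = 58%.
- Assumed 80% (d = 2.802). Equal groups: 50.8% each, exactly one 50%. At 25:75: 28.8% and 67.9%, exactly one 58%.

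**Comparator.** Under the same uniform effect, a valid interaction test at two-sided 0.05 signals a difference in 5% of cases.

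**Power of the interaction test.** For a true 5-point difference between equal groups at SD 12 and N = 100: z = 5 / (12 × √(1/50 + 1/50)) = 5 / 2.4 = 2.08, so power is Φ(2.08 − 1.96) ≈ 55%.

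All these figures use unadjusted p<0.05. The effect of the separate FDR categories is not quantified.

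**The case against.** The strongest reply is that the plan never proposes to infer a group difference from significance in one group and not in the other. A reader might take the similar-trend aim in SAP 12 to govern the secondary runs, and conclude that the plan intends that inference. The text does not support this: the aim is stated for the co-primaries and paired with the interaction term, while the within-group runs are introduced as a separate addition. This stands. The defect is a missing comparison, not a faulty decision rule.

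The subgroup work is also labelled exploratory, is to be read with caution, and has FDR control in each group, with a table of p-value counts. These protections are real. But FDR control within a group limits false discoveries there. It does not stop a true, uniform effect from passing in one group and missing in the other. Nor does caution provide an estimate of the difference.

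The outcomes overlap: time 70-180 is what remains after time >180 and time <70, so the co-primary interaction on daytime time >180 informs part of the picture. It does not directly address HbA1c, insulin or BMI.

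Finally, the 25% share is a recruitment floor and not an expected split. It is set on screening point-of-care HbA1c, whereas Protocol 4.1.2 defines a central-laboratory baseline drawn at randomization. It therefore may not bound the analyzed HbA1c groups, and it says nothing about age. This also stands.

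**Conclusion.** The gap is real: the plan produces within-group p-values for the secondary efficacy outcomes and no valid comparison between groups for any of them. With the plan's hyperglycemia inputs and 100 completers, a uniform effect appears in one group only about 29% of the time at 50:50 and 49% at 25:75. The 47-58% range for a secondary outcome depends on assumed overall power of 80-90% and splits from 50:50 to 25:75. It should not be read as a forecast for this trial, because the documents give no secondary effect sizes or SDs. All the figures assume the same effect and SD in both groups.

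A reader might go further and infer that the secondary tables are bound to show many spurious age-specific or HbA1c-specific effects, or that the within-group p-values must be removed. Neither follows. The first depends on unknown power and on how the tables are read, and the second is not needed to close the gap. The change is worth making because the remedy is specific and the plan already uses it for the co-primaries.

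**What to change.** In SAP 12, for each secondary efficacy outcome:

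- Add a treatment-by-age-group term and a treatment-by-HbA1c-group term to the full-cohort model, using the two-level groups already defined.
- Report the treatment difference with its 95% CI in each group, beside the interaction p-value.
- State that any claim of a subgroup difference rests on the interaction test and not on within-group significance.

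In SAP 13, add an FDR category for these interaction p-values.

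Dropping the within-group p-values is optional. Protocol 10.12 also calls for those separate analyses, so dropping them would require aligning it with the SAP.

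The cost is extra analysis work, using the same approach as for the co-primaries, and no new data. The interaction tests will have limited power, about 55% in the example worked above, so a non-significant interaction must not be read as proof of equal effects. The group-specific CIs make that uncertainty visible.
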